Our pre-specified inclusion criteria will minimize selection bias since infant appearance at birth, rather than actual cord management, determines which infants are included. Allocation bias will be prevented since all non-vigorous infants will receive the same treatment during the prescribed epoch. It is impossible to blind obstetrical providers or parents to the assigned treatment arm. To avoid clinical team bias we will request documentation of the specific intervention (UCM or ECC) not be included in the infant's medical record. Since cord management is not routinely provided in the medical record we have specifically avoided any inclusion of the management to avoid downstream bias once the study has begun. In order to prevent admission bias in either of the prescribed epochs, we have outlined pre-specified criteria that will constitute a NICU admission for purposes of this study, see appendix 2.

Specific Aim 2 (SECONDARY) Compare the safety and efficacy profiles of non-vigorous newborns 35-41+6 weeks GA delivered receiving UCM vs. ECC during their birth hospitalization and at 24 months corrected age.

H2: Compared to ECC subjects, UCM subjects will have higher cerebral oxygen saturations at 10 minutes of life (sub-study at three (3) sites, n=20).

Rationale: Caregivers and researchers raised theoretical concerns that the UCM technique may deliver blood rapidly toward a non-vigorous newborn predisposing them to higher rates of brain injury or dislodging cellular debris into the brain. However, of the 13 studies on term infants comparing UCM to ECC, none have reported adverse outcomes. All demonstrated improvements similar to DCC with increased red cell mass (measured by hematocrit or hemoglobin) improved blood pressure, increased pulmonary blood flow and improved ferritin at 6 weeks to 6 months of age with UCM. Nevertheless, careful assessment of safety is essential. Immediate physiological measurements on a subset (n=20) of infants of the three sub-study sites where the use of NIRS is standard of care, University of Alberta, SMBHWN and SGH to establish the safety and efficacy of UCM. This aim will further test our hypotheses that infants in the UCM group will have improved early cardiac and cerebral hemodynamics within the first 10 minutes.

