As this is a cluster randomized crossover trial where the standard of care for every non-vigorous infant will be the same over a year at each site it is unlikely there will be a significant portion of newborns that will receive the wrong allocation based on the cluster. The inclusion/exclusion criteria were designed to be minimal and pragmatic for providers to decide readily if the infant should receive the treatment arm. The outcomes for infants with protocol violations will be measured and analyzed according to original allocation by intention-to-treat principles. Only newborns who meet pre-defined exclusion criteria (i.e. cord avulsion or congenital anomaly) will be excluded from the primary analyses, although we will verify that there is not a differential occurrence by treatment from procedure. This strategy was successful in our previous trials.

In prior cord milking trials conducted by [name], protocol violation rates for UCM (milking <4 times) were <5 percent. To ensure optimum compliance, he conducted extensive education and certification of our obstetricians in the delivery room. For the proposed trial, the site investigators all have significant experience with UCM and have equipoise of both cord management techniques. All lead perinatal investigators agreed on the techniques and will ensure their colleagues are adequately trained on the maneuvers to minimize site variability. Sites also agreed on institutional policies to video record the UCM techniques at initial startup to minimize site-to-site and inter-observer variations. Videos will be kept at local sites and used solely for study specific training purposes. Videos will be kept secure per local institutional policies. Site PIs will be considered 'certified' upon agreement of the lead site PI (AK). Training videos and materials will be disseminated to be used as a refresher for delivery room staff, fellows, and attending neonatologists. Monthly teleconference meetings will be conducted to examine site comfort with, and performance of UCM techniques, as well as record keeping, and other study or regulatory issues.

V. STATISTICS

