Sample size and power calculation We estimated that a sample size of 1200 across ten sites would be needed to test efficacy of UMC versus ECC for the primary outcome. This was based on the following assumptions: a clinically meaningful 35% reduction in NICU admissions (16.25% for UCM versus 25% for ECC), a two-sided type I error alpha = 0.05, 85% power, 0.02 rho (within cluster within period correlation), 0.02 eta (within cluster between period correlation), and a correction factor (4 x cluster size) for the small number of clusters(51).

For the longer-term neurodevelopment outcome scores, we estimated that a sample size of 1200 across ten sites, with an assumed two-sided type I error alpha = 0.05, 0.02 rho, 0.02 eta, a correction factor (4 x cluster size) for the small number of clusters, and Cohen's d = 0.25, power ranges from 79% to 87% when assuming a range in lost to follow-up from 20% to 10%. The original sample size for this trial was 1000. However, at the first DSMB meeting in May 2019 only four sites had begun enrollment and enrollment was nearing completion of the crossover point (nearly 2/3 complete in the first arm), and two sites were unable to obtain IRB approval. Therefore in conjunction with the DSMB, the decision was made to reassess the sample size calculation for ten sites.

Feasibility Based on the numbers of newborns at each of ten sites, we expect a total of approximately 1500 newborns with a 1-minute Apgar of ≤ 3 per year. Estimating conservatively that at least 50% will be classified as non-vigorous, a 2-year period of recruitment would be required. The ten sites agree to recruit and each one has provided an estimated number 35-41+6 weeks infants delivered per year.

Statistical Approaches for Testing Hypotheses

All statistical analyses will be based upon the total cohort of patients randomized into the trial. Patients will be included in the treatment group to which they were randomly assigned. We will use the intent-to-treat analysis to determine treatment difference between the UCM and ECC groups.

Descriptive statistics (counts and proportions for categorical variables and means and standard deviations or medians and interquartile ranges for continuous outcomes) will be used to compare baseline demographic, physiologic and clinical

outcomes between the two treatment groups. All statistical tests are two-sided with alpha = 0.05.

Analysis of Primary Outcome (NICU Admission)

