The eligibility will be determined for each child at birth. Any vigorous or crying infant will receive usual care and will not be included in the study. All high-risk deliveries attended by the Pediatric team will be screened. If the infant is determined to be non-vigorous and needs resuscitation, the baby receives the treatment arm as assigned per the trial and will be added to the screening log as eligible for follow up. If the infant did not meet any exclusion criteria, the site's designated research coordinator or their designee will approach parents following delivery and resuscitation to explain the remaining portion of the study (ongoing data collection, and periodic contact via phone, text, letter or email for developmental follow-up studies). Each site will be responsible for maintaining their own master screening log. The purpose is for each screened patient to be assigned a study number to track eligibility, informed consent and data collection. The log with the study numbers and site patient identifiers will be kept in a secure, limited access area at each center. Only investigators and research personnel who are involved with the study will have access to the site specific log.

Inclusion Criteria

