As a pragmatic trial, all deliveries that do not meet exclusion criteria will be included. We acknowledge that anticipating resuscitation based on fetal (abnormal fetal heart rate tracing) or delivery (need for instrumentation or meconium) criteria do not accurately predict the need for resuscitation. The determination for eligibility will be determined for each child at birth by the obstetrical provider. Any vigorous or crying infant will receive usual care (i.e., delayed cord clamping) and will not be included in the study. If the infant is non-vigorous as determined by usual practice the baby receives the treatment arm as assigned per the trial. **Non-viable infants or infants of unknown viability will not be included in the trial, only viable infants in distress. Infants born in extremis for whom no additional treatment will be offered by the attending neonatologist will not be enrolled in this trial. The individuals making the assessment of the infant at birth (Obstetrical Residents, Obstetrician, Midwife or other perinatal provider) are not co-investigators or key personnel so they will have no conflict of interest regarding enrollment.** Based on annual deliveries and the number of infants with a low Apgar score ≤ 3 , we anticipate this will occur in about 3 percent of all term/near-term deliveries at each site.

- Non-vigorous Infants delivered at 35-41+6 weeks GA

Exclusion Criteria

- Known major congenital or chromosomal anomalies of newborn
- Known cardiac defects other than small ASD, VSD and PDA
- Complete placental abruption/cutting through the placenta at time of delivery
- Monochorionic multiples
- Cord anomaly (i.e. cord avulsion, true knot)
- Presence of non-reducible nuchal cord
- Perinatal providers unaware of the protocol

- Incomplete delivery data
- Infants born in extremis, for whom additional treatment will not be offered

This protocol will not adversely affect the rights and welfare of subjects, and will involve no more than minimal risk to subjects. This study meets the criteria of 45 CFR 46 Subpart D a) 404 the research is not greater than minimal risk.

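### Three exclusions judged at delivery are prompted on the delivery form only as reasons for wrong treatment, so unequal removal by arm is possible and should be prevented by identical recording in both epochs

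*Combined protocol and SAP*

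**What the plan says.** **Who is analysed.** Section IV (Maintaining Adherence to Algorithms and Minimizing Deviation from Protocol) keeps protocol violations as allocated, but adds: "Only newborns who meet pre-defined exclusion criteria (i.e. cord avulsion or congenital anomaly) will be excluded from the primary analyses". It continues: "although we will verify that there is not a differential occurrence by treatment from procedure". No method or consequence follows there or elsewhere in the text. Section V (Statistical Approaches for Testing Hypotheses) says: "All statistical analyses will be based upon the total cohort of patients randomized into the trial".

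**Who judges eligibility.** Section VI (Inclusion Criteria): "As a pragmatic trial, all deliveries that do not meet exclusion criteria will be included", and "The determination for eligibility will be determined for each child at birth by the obstetrical provider". Section IV (Prevention of Bias in an unblinded trial): "It is impossible to blind obstetrical providers or parents to the assigned treatment arm". Under Preparation of sites for the trial (Section III), each site learns its arm before starting.

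**What is recorded.** The exclusion list includes complete abruption or a cut placenta, cord anomaly such as avulsion, and "Presence of non-reducible nuchal cord". On the Appendix 3 form, abruption or cut placenta, cord tear and non-reducible nuchal cord have boxes only in the field asking why the infant did not get the correct treatment. Each site also keeps a master screening log: "The purpose is for each screened patient to be assigned a study number to track eligibility, informed consent and data collection". Section VII (Waiver of HIPAA Authorization) gives that log a field for the reason an infant was not enrolled.

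**The concern.** In a UCM epoch, an infant whose cord has to be cut at once has not received the assigned treatment. The form field applies, the reason is ticked, and the infant can be matched to an exclusion. In an ECC epoch, the same infant clamped early has received the assigned treatment. The field does not apply and nothing else on the form prompts the event.

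If exclusions were drawn from that field, these infants would leave the UCM arm more often than the ECC arm. In an unblinded trial, unequal removal after assignment can move the primary relative risk with no treatment effect. The planned check on differential occurrence is the right idea, but as written it has no method, and no action follows from its result.

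**Working it through.** **1. The plan's own figures.** Section V gives 25% v 16.25%, two-sided alpha 0.05, 85% power, rho = eta = 0.02, ten sites and a correction of 4 x cluster size.
- Cluster size: 1200/(10 x 2) = 60 per site-period.
- Unpooled two-proportion size: 379.5 per arm.
- Design effect: 1 + 59 x 0.02 - 60 x 0.02 = 0.98.
- Total: 2 x (379.5 x 0.98 + 4 x 60) = 1224, against 1200 stated. This reproduces within 3%.
- Treated as 600 independent infants per arm, power would be 96.5%. A calculation at the plan's stated precision should therefore use about 379.5 effective infants per arm, which gives 85%.

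**2. Bias from unequal removal.** Let f be the share of infants with one of the three events, r their NICU risk and s the share of ECC events captured. All UCM events are assumed removed, with no true effect and 25% overall risk. The documents give none of f, r or s.
- UCM rate U = (0.25 - f r)/(1 - f)
- ECC rate E = (0.25 - s f r)/(1 - s f)
- z = (E - U)/SE, with SE^2 = U(1 - U)/[N(1 - f)] + E(1 - E)/[N(1 - s f)]

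Worked case, f = 5%, r = 80%, s = 50%:
- U = (0.25 - 0.04)/0.95 = 22.11%; E = (0.25 - 0.02)/0.975 = 23.59%.
- RR 0.937; difference 1.48 percentage points.
- N = 379.5: SE = 0.0311, z = 0.48, two-sided rejection 7.7%.
- N = 600: z = 0.60, rejection 9.2%.

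| s | f | r | U | E | RR | Rejection, N = 379.5 | Rejection, N = 600 |
|---|---|---|---|---|---|---|---|
| 100% | any | any | equal | equal | 1.000 | 5.0% | 5.0% |
| 75% | 2% | 60% | 24.29% | 24.47% | 0.993 | 5.0% | 5.1% |
| 75% | 5% | 80% | 22.11% | 22.86% | 0.967 | 5.7% | 6.1% |
| 50% | 2% | 60% | 24.29% | 24.65% | 0.985 | 5.2% | 5.2% |
| 50% | 5% | 60% | 23.16% | 24.10% | 0.961 | 6.0% | 6.7% |
| 50% | 5% | 80% | 22.11% | 23.59% | 0.937 | 7.7% | 9.2% |
| 50% | 2% | 15% | 25.20% | 25.10% | 1.004 | 5.0% | 5.0% |
| 50% | 5% | 15% | 25.53% | 25.26% | 1.011 | 5.1% | 5.1% |

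At half capture with r = 60-80%, the shift is 0.36 to 1.48 points, or 4% to 17% of the planned 8.75.

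**3. Would a check on counts find it?** Assume a two-sided Fisher exact test at 5% with 600 per arm, since the plan names no test.
- 12 v 0 exclusions: p = 0.0005. Gross imbalance is exposed.
- 12 v 6: p = 0.23; difference 1.0 point (95% CI -0.4 to 2.6).
- Power at s = 50%: 22% (f = 2%) to 58% (f = 5%).
- Power at s = 75%: 7% to 15%.

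**The case against.** **The screening log.** This is the strongest defence. Under Eligibility criteria (Section VI), checking exclusions is a step for research staff before they approach parents. Every screened infant is numbered to track eligibility, and reasons for non-enrolment are logged. These steps are the same in both epochs, and no text says the Appendix 3 field decides exclusion. Appendix 1 also lists infant and delivery risk factors for all eligible infants, though it does not say whether they include these events. This stands: a reader might infer that exclusions are in fact applied only in UCM epochs, and the documents do not support that. What remains is that nothing requires the three events to be sought and recorded alike in both epochs. The intervention flow diagram is not shown and could not be checked.

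**The analysis set.** A reader might see a contradiction between removing excluded infants and analysing the total randomized cohort. The passages reconcile as eligible infants analysed by assigned epoch, and an infant who is both a deviation and an exclusion naturally follows the exclusion rule. Stating this in one sentence is a clarification only.

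**The check.** The protocol refers to a Statistical Analysis Plan and a Manual of Operations. If either exists separately, the method may be there.

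**Size.** A reader might infer a large bias in favour of UCM. A relative risk as low as 0.78 needs removal from UCM only, f = 10% and r = 75%, and a simple count would expose that pattern. The direction also depends on whether these infants' NICU risk is above 25%, which the documents do not say.

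**Conclusion.** The point holds as a cheap improvement. The form's prompting is asymmetric between epochs, the judgement is unblinded, and the infants concerned leave the primary analysis. Unequal removal is possible but not shown.

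Under the stated assumptions (f 2-5%, r 60-80%, half of ECC events captured, all UCM events removed), the relative risk under no effect is about 0.985 to 0.94. The rejection rate is about 5.2-7.7% at precision matched to the stated 85% power, or up to 9.2% without the small-cluster correction. With three-quarters capture it is at most 5.7% at matched precision. Equal capture gives no bias, and r below 25% reverses it slightly. Because a significance test of counts would often miss partial under-recording, identical recording protects better than the check alone.

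**What to change.** 1. **Record alike.** Make the three events yes/no items for every non-vigorous infant in both epochs, whatever treatment was given. For infants already enrolled, abstract them identically in both epochs from the permitted records (delivery room record, infant's chart). Decide exclusions without knowledge of NICU status.
2. **Sensitivity analysis.** Pre-specify an analysis of all assigned non-vigorous infants of 35+0 to 41+6 weeks with outcome data. Remove only opt-outs and conditions established before, or independently of, delivery-room judgement: known major anomalies, known cardiac defects and monochorionic multiples. Infants born in extremis are also classified after birth in an unblinded room, so report them by arm and analyse with and without them. Use the Appendix 2 definition of NICU admission where it can be obtained. Otherwise label the outcome as any NICU admission, because the log's NICU field is not the trial endpoint.
3. **Define the check.** Report exclusions by reason, arm and site-period, with a confidence interval for the difference, and read the primary result beside analysis 2.
4. **Clarify.** State the analysis set in one sentence in Sections IV and V.

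**Cost.** New form items come late: Version 1.8 is dated November 2020 and recruitment was planned to end in March 2021. Much of the work would be abstraction, which may be incomplete because Section IX bars the mother's chart. The waiver data set covers eligible subjects only, so its wording may need extending. The fix changes no planned sample size, alpha or power for the primary analysis. In the sensitivity analysis only, if 2-5% of UCM infants cannot be milked and gain nothing, the planned effect falls to 8.75 x 0.98 = 8.58 or 8.75 x 0.95 = 8.31 points, and 85% power to about 84% or 81%.

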Aims/Hypotheses	
Specific Aim 1 - (PRIMARY): Compare the incidence of admission to the NICU in 35⁰-41⁶ week GA non-vigorous newborns receiving Umbilical Cord Milking (UCM) to those receiving Early Cord Clamping (ECC).
 
H1: Compared to ECC subjects, UCM subjects will have a decreased incidence of NICU admission (based on predefined criteria).
 
Specific Aim 2 (SECONDARY): Compare the safety and efficacy profiles in 35⁰-41⁶ week GA non-vigorous newborns receiving UCM to those receiving ECC. Compared to ECC subjects, UCM infants will have:
 
H2: Higher cerebral oxygen saturations in the first 10 minutes of life (sub-study at two (2) sites, n=20).
 
H3: Receive a greater placental transfusion as estimated by hemoglobin levels by 48 hours of life and better blood pressure; will not have increased rates of hyperbilirubinemia compared to ECC subjects; will have decreased resuscitation interventions, level of HIE, use of therapeutic hypothermia, use of volume expanders, and length of hospitalization.
 
H4: Will have improved developmental outcome scores on the Ages & Stages Questionnaire, Third Edition (ASQ-3); UCM subjects will have a lower rate of medium to high risk scores on the MCHAT at 2 years of age.
 
H5: Better cardiac function as measured by echocardiography at 12 hours of life (sub-study at two (2) sites, n=200).

Design and Sample Size	This prospective multi-national cluster randomized crossover (CRXO) trial randomizes by hospital wherein each institution is randomized over time to each arm of the study n=1200 infants – 600 UCM/600 ECC
Inclusion Criteria	
 Non-vigorous newborns born between 35⁰-41⁶ weeks gestation
Exclusion Criteria	
 Known major congenital or chromosomal anomalies of newborn Known cardiac defects other than small ASD, VSD and PDA Complete placental abruption/cutting through the placenta at time of delivery Mono-chorionic multiples Cord anomaly (i.e. avulsion or true knot) Presence of non-reducible nuchal cord Perinatal providers unaware of the protocol Incomplete delivery data Infants born in extremis, for whom additional treatment will not be offered

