Although our hypothesis specifies 24 months as a primary endpoint, we will complete developmental assessments at 6, 12 and 24 months using the age and language appropriate Ages and Stages, 3rd ed. Questionnaire (ASQ-3). The parent or care giver completes the questionnaire with assistance by the site follow-up team as needed. At 24 months of age children will also be screened with the Modified Checklist for Autism in Toddlers (M-CHAT-R), a screening tool for autism. Various methodologies to enhance retention are described below.

The ASQ-3 is a developmental screen used worldwide for children 2 to 60 months of age and covers five developmental subscales (communication, problem-solving, fine motor, gross motor, personal-social). It has been shown to have good internal consistency and validity. Compared with the gold-standard Bayley Scales of Infant Development-II (BSID-II), sensitivity of the ASQ-3 is moderate (78%) for any delay and very high (92-100%) for severe delay. Compared to more recently published BSID-III norms, the ASQ-3 questionnaire has excellent negative predictive value (NPV, 98%) with subscale specificities ranging from 92% to 96%.

All parent questionnaires will be offered online via ASQ-3 online. In the event that a family prefers or does not have

access, a paper copy can be mailed. Survey results and feedback will be provided to the parents by the follow-up team. If a problem is identified, participants will be referred to their pediatrician or the site's High-Risk Infant Follow Up clinic for further evaluation. All surveys are published in both English and Spanish, but will be translated into those languages most commonly spoken at each site. Non-English translations, and certification of translation, will be provided for IRB review and approval upon PI receipt of the stamped IRB approved English versions prior to use in the study.

The M-CHAT-R is a parent-report screening tool used to screen for autism. Its goal is to maximize sensitivity and thus to detect as many cases of ASD as possible. It has a high false-positive rate meaning that not all children who score at risk will be diagnosed with ASD. The 20-item questionnaire asks for yes or no answers. If the total score is 0-2, the child is considered low-risk. If the score is 3-7, the child is considered medium-risk while a score of 8-20 indicates high risk.

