Secondary outcomes (use of therapeutic hypothermia, use of volume expanders, hemoglobin, bilirubin, death, and neurodevelopmental follow up scores) will be analyzed using similar multivariable procedures accounting for the study design as for the primary outcome to test treatment effects. Analyses will estimate relative risks and 95% confidence intervals for binary outcomes and means or mean differences and 95% confidence intervals for continuous outcomes. Secondary outcomes will be evaluated for missing data and those with and without missing data will be compared. Multiple imputation analysis will be conducted as warranted. Analyses will also evaluate death as a competing risk. No adjustment for multiple comparisons of secondary outcomes is planned.

Exploratory Analyses

Several outcomes are identified as exploratory (level of HIE, blood pressure, length of hospitalization, resuscitation interventions, and placental pathology). These analyses will focus on descriptive statistics rather than hypothesis testing. Likewise any evaluations of subgroup differences by treatment group (other than race/ethnicity as mentioned previously) will be explored in secondary analyses for descriptive purposes and solely for purposes of generating hypotheses for future studies.

Follow up Study- While all secondary and exploratory outcomes that occur during the delivery hospitalization will be presented in the primary paper, all subjects will continue to be followed until 24 months of age to determine their long-term outcome. The sample size is powered to detect differences in their Ages and Stages Composite and MCHAT scores.

Substudies for cerebral oxygenation and echocardiography will be reported as separate projects on clinical trials.gov and analyzed independently.

VI. Recruitment

Eligibility criteria

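### The plan names no analysis that uses the 6- and 12-month ASQ-3 scores for the 24-month comparison, and it leaves imputation conditional although 10–20% loss is expected

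*Combined protocol and SAP*

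**What the plan says.** Under Neurodevelopmental Follow-up Strategy (section IV), 24 months is the endpoint of the hypothesis, but "we will complete developmental assessments at 6, 12 and 24 months" with the ASQ-3. Appendix 1 lists the same three ages. The M-CHAT-R is given at 24 months only.

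The analysis text is in section V, Analysis of Secondary Outcomes. The follow-up scores, with the other secondary outcomes, "will be analyzed using similar multivariable procedures accounting for the study design as for the primary outcome". Infants with and without missing data are to be compared, and "Multiple imputation analysis will be conducted as warranted". No trigger, imputation model or predictors are given. No visit term or within-child covariance is named, and the 6- and 12-month scores are given no role. Death is to be evaluated as a competing risk.

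The model carried over is the one for NICU admission. That outcome is measured once and is expected to have almost no missing data. Its terms are treatment, period, cluster and cluster by period, with allowance for siblings from one pregnancy.

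On power, Sample size and power calculation states that "power ranges from 79% to 87% when assuming a range in lost to follow-up from 20% to 10" per cent. The Follow up Study paragraph says the trial is powered for the ASQ composite and M-CHAT scores.

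**The concern.** A missing-data approach that suits an outcome with almost no gaps is being applied to one that is expected to lose 10–20% of infants. Conditional imputation with no stated trigger leaves the main handling of that loss to be decided after the data have been seen.

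Informative loss is plausible. Parents cannot be blinded, each ASQ-3 result is fed back to them, and children with problems are referred. An earlier score may therefore influence whether the 24-month form comes back. If that happens differently in the two arms, a comparison of infants with a 24-month score is biased. The earlier scores are the information best placed to correct it, and the trial already collects them.

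Infants lost after 6 or 12 months also carry some information on the 24-month contrast, and the plan does not commit to using it.

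**Working it through.** **Inputs from the documents.** 1200 infants at ten sites ("For the longer-term neurodevelopment outcome scores, we estimated that a sample size of 1200 across ten sites"), split "n=1200 infants – 600 UCM/600 ECC". Tests: "All statistical tests are two-sided with alpha = 0.05". Follow-up assumptions: "0.02 rho, 0.02 eta, a correction factor (4 x cluster size) for the small number of clusters, and Cohen's d = 0.25".

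**1. Reproducing the stated power.**
- Infants per site per period: m = 1200/(10 × 2) = 60.
- Design effect: 1 + (m − 1)rho − m·eta = 1 + 59 × 0.02 − 60 × 0.02 = 0.98.
- Small-cluster correction: 4 × 60 = 240, taken off each arm.
- Standard error in SD units: √(2 × 0.98/(n − 240)), where n is the number per arm with a 24-month score.
- Power: Φ(0.25/SE − 1.96).

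| Loss | n per arm | SE | Power | Stated |
|---|---|---|---|---|
| 20% | 480 | √(1.96/240) = 0.0904 | 79.0% | 79% |
| 10% | 540 | √(1.96/300) = 0.0808 | 87.1% | 87% |

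Other readings of the correction do not match. Without it, power is 97.5% and 98.6%. With 240 taken off the total rather than off each arm, it is 92.3% and 95.5%. So the plan's figures count only infants with a 24-month score. With no loss, power would be 92.3%.

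**2. Power if earlier scores are used.** Let n1 be the infants per arm with a 24-month score and n2 those with only an earlier score, so n2 = 600 × loss × f, where f is the share of lost infants with an earlier score. Let R be the correlation of the earlier with the 24-month score. Under a normal model with monotone missingness, the effective number per arm is n1/(1 − R²·n2/(n1 + n2)). R and f are not in the documents and are assumed.

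Example: 20% loss, f = 1, R = 0.5 gives 480/(1 − 0.25 × 120/600) = 480/0.95 = 505.3, and power of 82.9%.

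| Loss | f | R = 0.3 | R = 0.5 | R = 0.7 |
|---|---|---|---|---|
| 20% (base 79.0%) | 0.25 | 79.4% | 80.2% | 81.3% |
| | 0.5 | 79.8% | 81.2% | 83.2% |
| | 1 | 80.4% | 82.9% | 86.3% |
| 10% (base 87.1%) | 0.25 | 87.3% | 87.5% | 87.9% |
| | 0.5 | 87.4% | 87.9% | 88.6% |
| | 1 | 87.7% | 88.6% | 89.9% |

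At f = 0 the gain is nil.

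**3. Bias when loss depends on the observed 12-month score.** Assume that 20% of one arm is lost with log-odds −0.7 per SD of the 12-month score, and that loss in the other arm is unrelated to the score. An intercept of −1.523 gives 20% loss. The mean 12-month score of those retained is then 0.130 SD too high, and the 24-month mean shifts by R × 0.130:
- R = 0.3: 0.039 SD (16% of d = 0.25)
- R = 0.5: 0.065 SD (26%)
- R = 0.7: 0.091 SD (36%)

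Regressing on the 12-month score within arm brings this to about 0. If the slope is the same in both arms, the complete-case difference is unbiased as well.

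**4. Bias when loss depends on the unseen 24-month score.** In a simulation with 20% loss, a steeper slope of −1.0 per SD and dependence in one arm only, the complete-case bias was about 0.17 SD in size. After using the 12-month score, 0.16 SD remained at R = 0.3, 0.13 at R = 0.5 and 0.10 at R = 0.7.

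**The case against.** **Inference from silence.** A reader might infer that the plan fixes a single-time-point, complete-case analysis and discards the earlier scores. The documents do not say so. The secondary-outcome text speaks of follow-up scores in the plural, provides for imputation and does not bar earlier scores from it. This stands: the defect is that no such use is specified, not that it is excluded.

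**Removing bias.** A reader might also infer that using the earlier scores would remove dropout bias. It does so only if loss is at random given the observed scores. Step 4 shows that more than half of the bias can remain otherwise. This stands, and it is why a sensitivity analysis for loss not at random belongs in the fix.

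**Size.** The follow-up goal is 90%, and at 10% loss the power gain is small. The ASQ-3 is collected only after consent, so infants never consented, or lost before 6 months, add nothing. With complete data, an unstructured repeated-measures model gives the same 24-month contrast. The bias at R = 0.5 (0.065 SD) is below one standard error (0.09) and rests on an assumed slope. All of this stands. Counting lost infants as contributing nothing is also an ordinary conservative planning convention, not an error in the power calculation.

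**Existing mitigation.** Repeated contacts to 24 months and telephone completion should limit loss. The plan's own power statement nevertheless allows up to 20%.

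**What the objections leave.** Imputation with no trigger, predictors or model, for an outcome the plan presents as powered, is still open to choice after the data are seen. A bias of 16–36% of the planned effect is not trivial merely because it is below one standard error.

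**Conclusion.** The concern holds in a limited form. The plan commits to no method that brings the 6- and 12-month ASQ-3 scores into the 24-month comparison, and its imputation is conditional and undefined. Specifying their use would reduce, not remove, dropout bias: by about 0.04–0.09 SD in the one-arm scenario of step 3, and by much less in proportion if loss depends on the unseen 24-month score. The power gain is secondary. For correlations of 0.3–0.5 and a quarter to all of lost infants having an earlier score, it is 0.4–3.9 points at 20% loss and 0.1–1.4 points at 10% loss. At a correlation of 0.7 with all lost infants having an earlier score, power reaches 86.3% and 89.9%. The correlations, shares and dropout slopes are assumptions; only the 79% and 87% starting points come from the plan. This is a worthwhile, inexpensive improvement to a secondary follow-up analysis and does not affect the primary outcome.

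**What to change.** In Analysis of Secondary Outcomes, name the ASQ-3 score to be analysed and make the main 24-month analysis one of the following:

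- **Repeated-measures mixed model** on the 6-, 12- and 24-month scores, with treatment by visit, period by visit and unstructured within-child covariance. It keeps the primary model's site, cluster-by-period and within-pregnancy terms, and the 24-month contrast is the reported effect.
- **Multiple imputation that is always run**, by arm, with site, period and the earlier ASQ-3 scores in the imputation model, followed by the design-based analysis.

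Use the same imputation for 24-month M-CHAT-R risk. Define the target population with respect to death, so that scores are not imputed for children who died without that being a stated choice. Keep the complete-case analysis as a sensitivity analysis, and add one for loss not at random, for example a range of shifts applied to the imputed scores by arm.

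Cost: SAP wording, more programming, and care in fitting the model with only ten clusters. No new data, visits or patients are needed.
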